9.4.2 Serious Adverse Events

Any SAE experienced by the subject from Visit 2 (Day 1) through Visit 10 (Month 12) is to be recorded on an SAE Form, regardless of the severity of the event or its relationship to study treatment.

Any SAE ongoing when the subject completes the study or discontinues from the study will be followed by the investigator until the event has resolved, stabilized, or returned to baseline status.

9.4.3 All Events

All events must be assessed to determine the following:

- If the event meets the criteria for an SAE as defined in Section 9.2.
- The severity of the event as defined in Section 9.7.1.
- The relationship of the event to study treatment as defined in Section 9.7.2.

9.5 Immediate Reporting of Serious Adverse Events and Pregnancies

In order to adhere to all applicable laws and regulations for reporting an SAE or pregnancy, the study site must formally notify the pharmacovigilance team within 24 hours of the study site staff becoming aware of the SAE or pregnancy. It is the investigator's responsibility to ensure that the SAE or pregnancy reporting information is emailed as described in Figure 3. It may be necessary for the pharmacovigilance team to directly communicate with the investigator if additional information is required.

After the initial SAE report, the investigator is required to proactively follow each subject and provide further information to the pharmacovigilance team on the subject's condition within 24 hours. New or updated information will be recorded on the SAE reporting form. The updated SAE reporting form should be sent to the pharmacovigilance team within 24 hours.

All additional follow-up evaluations must be reported to the pharmacovigilance team. Such data should be sent by email (Figure 3) within 10 calendar days. All SAEs will be followed until the investigator and Sponsor agree that the event is satisfactorily resolved.

Figure 3 Reporting Information for SAEs and Pregnancies

To report initial or follow up SAE or Pregnancy information email a copy of the SAE or Pregnancy report form to the following:

Safety

Email: [contact]

[contact]

9.6 Death

The death must be recorded on the appropriate eCRF. All causes of death must be reported as SAEs. The investigator should make every effort to obtain and send death certificates and autopsy reports to the pharmacovigilance team.

9.7 Evaluating AEs and SAEs

9.7.1 Severity

The following definitions should be considered when evaluating the severity of AEs and SAEs.

Mild	Event is noticeable to the subject, but is easily tolerated and does not interfere with the subject's daily activities
Moderate	Event is bothersome, possibly requiring additional therapy, and may interfere with the subject's daily activities
Severe	Event is intolerable, necessitates additional therapy or alteration of therapy, and interferes with the subject's daily activities.

For AEs that change in intensity, the start and stop date of each intensity should be recorded.

An AE that is assessed as severe should not be confused with a SAE. An event is defined as 'serious' when it meets one of the pre-defined outcomes as described in Section 9.2 Definition of a SAE.

9.7.2 Relationship to Investigational Product or Procedure

The following definitions should be considered when evaluating the relationship of AEs and SAEs to the study product or procedure:

Definitely Related	Event with plausible time relationship to product/procedure Cannot be explained by disease or other drugs Event definitive pharmacologically or phenomenologically (i.e., an objective and specific medical disorder or a recognized pharmacologic phenomenon)
Probably Related	Event with reasonable time relationship to product administration/procedure Unlikely to be attributed to disease or other drugs
Possibly Related	Event with reasonable time relationship to product administration/procedure Could also be explained by disease or other drugs
Not Related	Event or laboratory test abnormality, with a time to drug intake that makes a relationship improbable (but not impossible) Disease or other drugs provide plausible explanation

9.7.3 Expectedness of Events

Expectedness of all AEs will be determined according to the Investigator's Brochure.

9.8 Procedures for Handling Special Situations

9.8.1 Pregnancy

Females should not become pregnant during the study period. If this occurs the subject should notify the investigator immediately. The investigator must report the pregnancy as outlined in Section 9.5. In addition, the investigator or study site staff must report the outcome of the pregnancy to the pharmacovigilance team.

9.8.2 Unmasking for Medical Emergencies

The need to unmask is not expected for this trial. If a need for unmasking arises, the treatment assignment may be unmasked and made available to the investigator, sponsor, and/or other study personnel involved in the conduct of the study, according to Unmasking Procedure (or other documents as applicable). In the absence of medical need, the treatment assignment will not be available to the above individuals until after the study is completed and the database is locked.

In the event of a medical need, the investigator will treat each subject, as medically required. If the investigator feels it is necessary to unmask a subject's treatment assignment after an emergency situation, the investigator may call the Medical Monitor and notify the Sponsor. The treatment assignment will be revealed on a subject-by-subject basis with the approval of the Medical Monitor and Sponsor, leaving the masking of the remaining subjects intact. The Sponsor

will make the final determination if the unmasking request will be granted. Once the unmasking request is granted the investigator will be provided with the treatment assignment. The investigator must also indicate in source documents and in the eCRF that the mask was broken and provide the date, time, and reason for breaking the mask. Any AE or SAE associated with breaking the mask must be recorded and reported as specified in this protocol.

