6.5 Trial Duration

An individual subject's participation in the study will last approximately 12 months after injection of study drug. All subjects completing 12-month visit will be invited to participate in a long-term safety study. Data from this study will be reviewed by the Medical Monitor on an ongoing basis in a masked fashion.

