10 STATISTICAL METHODS AND DATA ANALYSIS

10.1 Study Reporting

There will be two reporting events for this study, one reporting when all subjects complete Month 6 visit and another reporting when all subjects complete the study. For the first reporting, when all subjects complete the Month 6 visit, data will be cleaned and locked at the subject visit level. The study will be unmasked for the 6 months efficacy and safety analyses. For the second data reporting, when all subjects complete the entire study, data will be cleaned, and the database will be locked.

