7 STATISTICAL METHODS

7.1 Study Reporting

There will be two reporting events for this study, one reporting when all subjects complete Month 6 visit and another reporting when all subjects complete the study (Month 12 visit). For the first reporting, when all subjects complete the Month 6 visit, data will be cleaned and frozen at the subject visit level. The sponsor will be unmasked for the 6 months efficacy and safety analyses. AE starting after the Month 6 visit will not be included for Month 6 reporting for better risk-benefit assessment. All other data after Month 6 visit will be included and reported as they are. For the second data reporting, when all subjects complete the entire 12-month study, data will be cleaned, and the database will be locked.

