9 PROTOCOL DEVIATIONS

Protocol deviation will be reviewed by the sponsor at on-going basis. The deviation file will include a description of the protocol deviations, as well as classification of major or minor. Major deviations will further be categorized by different deviation categories. Number and percentage of subjects with major protocol deviations will be summarized by deviation category. For the protocol deviation summaries, any data collected at and after rescue visits will not be used.

Protocol deviations, including both major and minor deviations, will be presented in a listing.

The final criteria for the per-protocol set, regarding which protocol deviations that warrant exclusion, will be determined during the blinded data review when all data on protocol deviations are available and before breaking the blind.

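### Protocol 9.8.2 withholds treatment assignment until study completion and database lock, but Protocol 10.1 and SAP 7.1 unmask at Month 6, with no statement of who stays masked to Month 12

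*Protocol*

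**What the plan says.** Three places say when assignment becomes known.

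- Protocol 9.8.2 allows assignment, when a need arises, to be "made available to the investigator, sponsor, and/or other study personnel involved in the conduct of the study". For the same people, when there is no medical reason to unmask, "the treatment assignment will not be available to the above individuals until after the study is completed and the database is locked".
- Protocol 10.1 plans two reports, "one reporting when all subjects complete Month 6 visit and another reporting when all subjects complete the study". For the first, data are locked visit by visit, and "The study will be unmasked for the 6 months efficacy and safety analyses". The database lock belongs to the second report.
- SAP 7.1 keeps the two reports, has the data frozen rather than locked at visit level, and says "The sponsor will be unmasked for the 6 months efficacy and safety analyses". It adds that data after Month 6, other than newly starting adverse events, go into the first report as they stand.

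SAP 15 declares no changes from the protocol-stated analyses. SAP 2 lets the SAP override the protocol on statistical analysis methods.

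On who stays masked, Protocol 6.5 says "Data from this study will be reviewed by the Medical Monitor on an ongoing basis in a masked fashion". Protocol 7.3 keeps investigators, subjects and study personnel masked, but in a section limited to recruitment, screening, rescreening and treatment. Protocol 6.3 provides unmasked team members to manage the treatment sequence.

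**The concern.** A trial labelled double-masked should have one answer to the question of who knows the assignment, and when. Here, carrying out the Month 6 report as written breaks the rule in 9.8.2, and neither document describes a barrier between the people who are unmasked and those still making judgements on subjects in follow-up.

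Several of those judgements continue to Month 12. Rescue keratoplasty has no numeric trigger: Protocol 8.3 rests on clinical decline, evaluation of symptoms and findings, and consultation with the Medical Monitor. Rescue rate and time to rescue are safety evaluations (SAP 4.2.2), and SAP 7.9 removes data at and after rescue from the tables, apart from separately summarised adverse events. A rescue decision influenced by knowledge of the arm would therefore alter both the rescue results and the later acuity and thickness data. BCVA and CCT at Months 9 and 12 are secondary endpoints. The sponsor may discontinue a subject for any reason (Protocol 7.4), may judge the causality of serious events (9.8.3) and reviews deviations on an ongoing basis (SAP 9).

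**Working it through.** **Step 1. Compare the rules.**

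| Source | Who | When assignment opens | State of the data |
|---|---|---|---|
| Protocol 9.8.2 | investigator, sponsor, other study personnel | study completed and database locked, unless medical need | final lock |
| Protocol 10.1 | the study, no limit on roles given | first report, after all subjects complete Month 6 | visit-level lock |
| SAP 7.1 | the sponsor | first report, same trigger | visit-level freeze |

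The sponsor is named in 9.8.2 and in SAP 7.1, so those two conflict outright. Protocol 10.1 conflicts with 9.8.2 for at least the sponsor, and for investigators and site staff too if it is read as opening the whole study. None of the three is written as an exception to another.

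**Step 2. What is protected.** Unmasking follows the last subject's Month 6 visit. Every Month 6 BCVA, and so every primary response, has been recorded by then.

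**Step 3. What is exposed.** Only events after the actual unmasking date. On the broad reading of 10.1, site assessments of BCVA, CCT, adverse events and rescue are exposed directly. On the SAP reading, exposure runs through the sponsor roles in Protocol 7.4, Protocol 9.8.3 and SAP 9, and through any sponsor contact with sites. Nothing limits the sponsor to aggregate results, and SAP 6.1 sorts listings by treatment group and then subject number, which ties each subject to an arm.

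**Step 4. Illustrative size.** There is no stated figure to reproduce, and the documents do not give the accrual time. Assume uniform enrolment over A months and unmasking d months after the last subject reaches Month 6, that is at A + 6 + d. A subject treated at time a reaches Month 12 at a + 12, which is later than unmasking when a > A − 6 + d. For d up to 3:

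- share with Month 12 after unmasking = min(1, (6 − d)/A)
- share with Month 9 after unmasking = min(1, (3 − d)/A)
- with d = 0 and A ≥ 6, share of Month 6 to 12 person-time after unmasking = 3/A

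| A (months) | Month 12, d = 0 | Month 12, d = 2 | Month 9, d = 0 | Person-time, d = 0 |
|---|---|---|---|---|
| 6 | 6/6 = 100% | 4/6 = 67% | 3/6 = 50% | 50% |
| 12 | 6/12 = 50% | 4/12 = 33% | 3/12 = 25% | 25% |
| 18 | 6/18 = 33% | 4/18 = 22% | 3/18 = 17% | 17% |

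The 2-month delay is also an assumption. It stands for the cleaning that both documents require before the first report.

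**The case against.** The strongest reply is that the three sentences can largely be read together. Section 9.8.2 sits under a heading on medical emergencies. Protocol 10.1 limits unmasking by its purpose, the Month 6 analyses, and SAP 7.1 uses the same sentence with the sponsor named. On that reading sites remain masked under 9.8.2 and only the sponsor's status is in conflict. Much of this stands, and it is why site exposure is called indirect under the SAP. It does not remove the conflict. The sentence in 9.8.2 governs the absence of medical need and so works as a general rule, and it names the sponsor. SAP 2 gives the SAP precedence on statistical methods, which does not obviously extend to who holds the codes.

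Four stronger readings are tempting but not supported.

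- **The primary result is compromised.** It is not, for the reason in step 2.
- **The Medical Monitor will be unmasked.** Protocol 6.5 says that role reviews data masked, with no Month 6 cut-off. What is missing is a statement that this continues through the Month 6 unmasking. The unmasking procedure and monitoring plan that the protocol mentions may cover it, but they are not among the documents reviewed.
- **The per-protocol set cannot be fixed in time**, because SAP 9 sets exclusions "when all data on protocol deviations are available and before breaking the blind". SAP 5.2 restricts exclusions to major deviations that affect the primary endpoint evaluation. A deviation after a subject's Month 6 visit cannot do so, so the relevant deviations are known before unmasking. Protocol 10.5 defines the set more widely, by study completion; that is a separate difference of definition.
- **Formal comparisons at Months 9 and 12 are invalidated.** SAP 13.2 compares treatments at Month 6 only and treats other timepoints descriptively. Safety has no formal tests (Protocol 10.8), the study is not powered, and p-values are nominal (SAP 7.3 and 7.5).

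**Conclusion.** The contradiction is real: Protocol 9.8.2 forbids, for the sponsor at least, what Protocol 10.1 and SAP 7.1 schedule. The plan also leaves unsaid who remains masked between the Month 6 report and final lock. The consequence is confined to follow-up after unmasking: Month 9 and 12 BCVA and CCT summaries, rescue rate and time to rescue, causality judgements and discontinuations. As written, those data cannot safely be described as double-masked.

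Under uniform accrual over 6, 12 or 18 months, at most 100%, 50% or 33% of subjects have their Month 12 visit after unmasking. An assumed 2-month cleaning period lowers this to 67%, 33% or 22%. Accrual weighted towards the end of enrolment would raise the shares; early withdrawal would lower them. These figures measure how much follow-up is exposed. They do not show that bias occurs or how large it would be. The point should be corrected, but it does not threaten the Month 6 analysis.

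**What to change.** Reconcile Protocol 9.8.2, Protocol 10.1 and SAP 7.1 to one rule that:

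- names the sponsor or reporting roles that receive assignments for the Month 6 report;
- states that subjects, site staff, BCVA and CCT examiners, the Medical Monitor (consistent with Protocol 6.5) and site-facing sponsor staff stay masked until the final database lock, except for medical-need unmasking under 9.8.2;
- states that no subject-level assignment, including listings sorted by arm, is released to masked roles.

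If this cannot be met, data collected after unmasking should not be described as double-masked, and the report should give the unmasking date and the roles unmasked.

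The cost is wording in three sections and an access list. The one downside is that some sponsor staff would see only aggregate results until Month 12. The Month 6 report, the visits and the analyses stay as planned.

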9.8.3 Regulatory Reporting

Suspected Unexpected Serious Adverse Reactions (SUSARs) are SAEs that are unexpected and judged by the investigator or the Sponsor to be associated to the study treatment administered. The Sponsor will report SUSARs to the appropriate authorities within the required regulatory timeframes. Reports of SUSARs will be made to IRBs, and investigators, as needed.

10 STATISTICAL METHODS AND DATA ANALYSIS

10.1 Study Reporting

There will be two reporting events for this study, one reporting when all subjects complete Month 6 visit and another reporting when all subjects complete the study. For the first reporting, when all subjects complete the Month 6 visit, data will be cleaned and locked at the subject visit level. The study will be unmasked for the 6 months efficacy and safety analyses. For the second data reporting, when all subjects complete the entire study, data will be cleaned, and the database will be locked.

10.2 Statistical Methods

Summaries for continuous variables will include the sample size, mean, standard deviation, median, minimum and maximum. Summaries for discrete variables will include frequencies and percentages. The baseline visit will be defined as the last non-missing measure prior to initiation of investigational treatment.

10.3 Unit of Analysis

The unit of analysis in this study will be the study eye for all efficacy and ocular safety summaries. Additionally, non-ocular adverse events (AEs) and medical history will be presented at the subject level.

The non-study eye safety summaries will also be presented as appropriate.

10.4 Sample Size Determination

This study is not powered to show statistical significance but will provide initial estimates and trends of the endpoints for use in future trial designs. The sample size will allow for safety information to be obtained, while still limiting the number of subjects exposed to the IP. Statistical analyses will be descriptive.

10.5 Analysis Sets

The Full Analysis Set (FAS) will be defined as all eligible subjects who received any amount of study drug during intracameral injection. All subjects in FAS will be analyzed according to the treatment they actually received.

Per Protocol Set (PPS) will be defined as all subjects completing the study without major protocol deviations.

The Safety Analysis Set will be the same as FAS.

10.6 Statistical Significance

All statistical testing will be done at the two-sided alpha level of 0.05. As this is a Phase 1/2 study, no adjustments to alpha will be made for testing of multiple comparisons and multiple endpoints. Statistical analyses will be descriptive.

10.7 Efficacy Analyses

For the primary endpoint and other binary endpoints, number and percentage of subjects, with associated 2-sided exact (Clopper-Pearson) 95% confidence intervals (CIs), will be presented by treatment in each category (response, non-response). The distribution of responders will be compared between treatment arms using a two-sided Fisher's exact test.

Analyses of change from baseline in BCVA, CCT and [REDACTED] will be conducted using the full analysis set and a restricted maximum likelihood based mixed-effect model for repeated measures to evaluate the effect over time. The dependent variable will be the change from baseline. The model will include treatment arm, categorical time, treatment arm by time interaction, and baseline value as a covariate.

10.8 Safety Analyses

All safety analyses will be conducted on the Safety Analysis Set. No formal statistical tests of treatment difference are planned.

AEs will be coded using the Medical Dictionary for Regulatory Activities TEAEs (i.e., AEs that begin or worsen in severity after initiation of study drug) will be summarized by treatment arm and overall, in the study eye. Non-ocular TEAEs will also be summarized. Additionally, TEAEs and serious AEs will be summarized in a similar manner by maximum severity and relationship to study drug and the surgical procedure.

Changes from baseline of quantitative measurements (ophthalmic evaluations, laboratory findings) will be summarized by treatment arm and timepoint.

11 STUDY MANAGEMENT AND DATA COLLECTION

11.1 Confidentiality

All trial subject data collected and processed for the purposes of this trial should be maintained by the investigator and his/her staff with adequate precautions as to ensure that the confidentiality of the data is in accordance with local, state, and federal laws and regulations.

Monitors, auditors and other authorized representatives of CRO drug safety, the Sponsor, the IRB/IEC approving this trial, the FDA, the Department of Health and Human Services, other domestic government agencies, and other foreign regulatory agencies will be granted direct access to the trial subject's original medical and trial records for verification of the data and/or clinical trial procedures. Access to this information will be permitted to the aforementioned individuals to the extent permitted by law.

A report of the results of this trial may be published or sent to the appropriate health authorities in any country in which the IP may ultimately be marketed, but the subject's identity will not be disclosed in these documents.

11.2 Source Documents

Source documents may include a subject's medical records, hospital charts, clinic charts, the investigator's trial subject files, as well as the results of diagnostic tests such as SD-OCT. The investigator's electronic copy of the eCRFs serves as the investigator's record of a subject's trial-related data.

11.3 Case Report Forms

All subject data will be captured in the subject source documents which will be transcribed to the eCRFs. The investigator is responsible for ensuring that trial data is completely and accurately recorded on each subject's eCRF, source documents, and all trial-related materials. All trial data should also be attributable, legible, contemporaneous, original, accurate and complete. Recorded data should only be corrected in a manner that does not obliterate, destroy, or render illegible the previous entry (e.g., by drawing a single line through the incorrect entry and writing the revision next to the corrected data). An individual who has corrected a data entry should make clear who made the correction and when, by adding to the correction his/her initials as well as the date of the correction.

Data entry of all screened and treated subjects will use software that conforms to 21 CFR Part 11 requirements and will be performed only by staff that have been trained on the system and have access to the system. Minimal data will be entered for screen failure subjects. An audit trail will be maintained within the electronic system to capture all changes made within the eCRF database. After the end of the trial and database lock, compact discs (CDs) or similar media containing copies of all applicable subjects' eCRFs will be provided to each investigator site to be maintained on file by the investigator.

